Slope i.e. average change per day from screening (“0”) to Day 2 [$BA_{CFU}(0-2)$] and from Day 2 to Day 14 [$BA_{CFU}(2-14)$] of the log CFU counts.	For each patient, linear and bilinear regression models will be fit, and the better fit model based on lower AIC will be used to estimate $BA_{CFU}(0-2)$ and $BA_{CFU}(2-14)$ of log CFU counts from screening to Day 2 and Day 2 to Day 14, respectively. An ANCOVA model will be used to quantify the evidence that the each of the treatment group means $BA_{CFU}(0-2)$ and $BA_{CFU}(2-14)$ is less than 0.
Slope of the time to sputum culture positivity (TTP) in the MGIT system from screening to Day 14 [$BA_{TTP}(0-14)$], from screening to Day 2 [$BA_{TTP}(0-2)$], and from Day 2 to Day 14 [$BA_{TTP}(2-14)$].	For each patient, linear and bilinear regression models will be fit, and the better fit model based on lower AIC will be used to estimate $BA_{TTP}(0-14)$, $BA_{TTP}(0-2)$ and $BA_{TTP}(2-14)$ of TTP from screening to Day 14, screening to Day 2 and Day 2 to Day 14, respectively. An ANCOVA model will be used to quantify the evidence that the each of the treatment group means $BA_{TTP}(0-14)$, $BA_{TTP}(0-2)$ and $BA_{TTP}(2-14)$ is less than 0.

Endpoint	Statistical Analysis
Slope of the log concentration of sputum LAM from screening to Day 14 [$BA_{LAM}(0-14)$], from screening to Day 2 [$BA_{LAM}(0-2)$], and from Day 2 to Day 14 [$BA_{LAM}(2-14)$].	For each patient, linear and bilinear regression models will be fit, and the better fit model based on lower AIC will be used to estimate $BA_{LAM}(0-14)$, $BA_{LAM}(0-2)$ and $BA_{LAM}(2-14)$ of log concentration of sputum LAM from screening to Day 14, screening to Day 2 and Day 2 to Day 14, respectively. An ANCOVA model will be used to quantify the evidence that the each of the treatment group means $BA_{LAM}(0-14)$, $BA_{LAM}(0-2)$ and $BA_{LAM}(2-14)$ is less than 0.
Secondary Safety	
Frequency of participants with adverse events (AEs) and frequency of AEs: overall, by seriousness, severity, body system, preferred term and relatedness to study drug.	The frequency of participants with and frequency of AEs will be summarized by treatment group. The incidence of AEs by seriousness, severity, body system, preferred term and relatedness to study drug will be summarized by treatment group.

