5.2 Secondary Objectives and Endpoint

Secondary EBA, safety and pharmacokinetics/pharmacodynamics (PK/PD) objectives and associated endpoints are summarized in Table 2.

Table 2. Secondary Objectives and Endpoint

Objectives	Endpoint
Early bactericidal Activity	
Demonstrate the EBA of the first 2 days (screening [“0”] to day 2) and of the remaining 12 days (day 2 to day 14) of 5 dose regimens of TBA-7371 monotherapy and HRZE, as assessed by CFU counts on solid media culture	
 • Slope, i.e. average change per day, from Screening (Day 0) to Day 2 [BA_{CFU}(0-2)] of the log₁₀CFU/mL counts; • Slope from Day 2 to Day 14 [BA_{CFU}(2-14)] of the log₁₀CFU/mL counts.
Demonstrate the EBA of 5 dose regimens of TBA-7371 monotherapy and of HRZE, as assessed by alternative methods: 
 • Time to sputum culture positivity (TTP) in Mycobacteria Growth Indicator Tube (MGIT) culture • Sputum lipoarabinomannan (LAM) assay 	
TTP:
 
 • Slope of the time to TTP in the MGIT system from Screening (Day 0) to Day 14 [BA_{TTP}(0-14)], • Slope of the TTP in the MGIT system from Screening (Day 0) to Day 2 [BA_{TTP}(0-2)]; • Slope of the TTP in the MGIT system from Day 2 to Day 14 [BA_{TTP}(2-14)]; 
LAM:
 
 • Slope of the log concentration of sputum LAM from Screening (Day 0) to Day 14 [BA_{LAM}(0-14)]; • Slope of the log concentration of sputum LAM from Screening (Day 0) to Day 2 [BA_{LAM}(0-2)]; • Slope of the log concentration of sputum LAM from Day 2 to Day 14 [BA_{LAM}(2-14)].
Safety	
Assess the adverse event (AE) profile of each dose regimen of TBA-7371 and HRZE over the 14-day treatment period.	Frequency from Day 1 through Day 15 of participants with AE and frequency of AEs: overall, by system organ class (SOC) and preferred term; by seriousness, intensity (severity), expectedness and relatedness to study drug.
Assess the impact on eye symptoms, visual acuity and color vision of each dose regimen of TBA-737 and HRZE over the 14-day treatment period.	
From Day 1 through Day 15:
 
 • Frequency of participants with any new (vs. Screening) eye symptom in one or both eyes. • Mean and frequency distribution of duration of each eye symptom. • Mean and frequency distribution of percentage of days with any eye symptom and each of the eye symptoms.

Table 2. Secondary Objectives and Endpoint

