where the parameters α and κ are the intercept and node parameter of the regression curve, respectively, the slopes β_1 and β_2 characterize the line of decline on or before the node ($t \leq \kappa$) and after the node ($t > \kappa$), respectively, and ε is the error term assumed to be independently distributed normally with mean zero and variance σ^2 . The parameters are constrained to aid in convergence as such: $\alpha > 0$, $1 < \kappa < 14$, $\sigma^2 > 0$, all $\in \mathbb{R}$. The SAS PROC NLMIXED procedure will be used to fit the bilinear regression model for individual participants in each treatment group. Suggested starting values for the parameters are $(\alpha, \beta_1, \beta_2, \kappa) = (6, 0, 0, 2)$ however a grid search approach can be followed to obtain sensible starting values. See SAS code in the Appendix which uses a grid search and picks the best fitting model.

If the bilinear regression model is selected, the average change in \log_{10} CFU/mL per day over 14 days will be estimated for each participant i by:

$$BA_{CFU}(0-14)_i = [\hat{\kappa}_i \hat{\beta}_{1i} + (14 - \hat{\kappa}_i) \hat{\beta}_{2i}] / 14$$

where $\hat{\beta}_{1i}$ is the estimated slope prior to the estimated inflection point $\hat{\kappa}_i$, and $\hat{\beta}_{2i}$ is the estimated slope after the estimated inflection point $\hat{\kappa}_i$. The parameters of main interest include the slopes $\hat{\beta}_{1i}$ and $\hat{\beta}_{2i}$, and the inflection points, $\hat{\kappa}_i$, and can be readily estimated using least squares. BA_{CFU}(0-14) can be estimated in PROC NLMIXED directly.

In the case where a subject does not have a non-missing measurement at Day 14, we have that

$$BA_{CFU}(0 - t_{last})_i = [\hat{\beta}_{1i} + (t_{last} - \hat{\kappa}_i) \hat{\beta}_{2i}] / t_{last}$$

where t_{last} is the last time point at which CFU was observed.

However, it is also likely that some of the participant specific \log_{10} CFU/mL count vs. time profiles will be better characterized using a simple linear regression model.

The form of the simple regression linear model is given by:

$$\log_{10} CFU/mL = \alpha - \beta_1 \cdot t + \varepsilon$$

where the parameters α and slope β_1 are the intercept and the slope that characterize the linear decline, and ε is the error term assumed to be independently distributed normally with mean zero and variance σ^2 . The SAS PROC NLMIXED procedure will also be used to fit a simple linear

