regression model for individual participants in each treatment group in order to ensure the Akaike information criteria (AIC) values for the linear and bilinear models are based on the same form of the likelihood function. Suggested starting values for the parameters are $(\alpha, \beta_1) = (6, 0)$ however a grid search approach can be followed to obtain sensible starting values.

If the linear regression model is selected, the average change in $\log_{10}\text{CFU}/\text{mL}$ count per day over 14 days will be estimated by the constant linear regression slope estimate, $\hat{\beta}_{1i}$, i.e.

$$BA_{CFU}(0 - 14)_i = \hat{\beta}_{1i}.$$

Therefore, for each participant, slopes will be estimated using both bilinear and simple linear regression models, and the better fit model based on lower AIC will be selected for that participant and used to estimate $BA_{CFU}(0-14)$. The $\log_{10}\text{CFU}/\text{mL}$ screening measurement used in the model will be the average of the two individual screening measurements. $BA_{CFU}(0-14)$ will be calculated for each participant within a treatment group individually, and then used as the response variable in an ANCOVA model, with a fixed effect for treatment group and screening $\log_{10}\text{CFU}/\text{mL}$ count as a covariate. Treatment group means from the ANCOVA model will be used to quantify the evidence that each of the treatment group mean $BA_{CFU}(0-14)$ is less than 0 (i.e., that the treatment group mean has a negative slope on average). The mITT population will be used for the primary efficacy analysis with analyses using the per-protocol population performed to assess the robustness of results. The SAS PROC MIXED procedure will be used to fit an ANCOVA model.

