11.1.2 Secondary Analysis

EBA measures $BA_{CFU}(0-2)$ and $BA_{CFU}(2-14)$ will be calculated from the bilinear regression model and assessed similarly as described for $BA_{CFU}(0-14)$ in [Section 11.1.1](#). There will be no adjustment for multiple comparisons and no formal success criteria for all secondary EBA measurements.

In order to estimate $BA_{CFU}(0-2)$ and $BA_{CFU}(2-14)$, the parameter κ is fixed at 2 so that the bilinear model used becomes

$$\log_{10} CFU/mL = \alpha - \beta_{1i} \cdot t + \varepsilon; \quad t \leq 2;$$

$$\log_{10} CFU/mL = \alpha + (\beta_{2i} - \beta_{1i}) \cdot 2 - \beta_{2i} \cdot t + \varepsilon; \quad t > 2$$

and therefore we have for participant i that

$$BA_{CFU}(0-2)_i = \hat{\beta}_{1i}$$

and

$$BA_{CFU}(2-14)_i = \hat{\beta}_{2i}.$$

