11.2 Secondary Efficacy Endpoints

11.2.1 Time to Sputum Culture Positivity

When time to sputum culture positivity for a participant is not concluded by Day 42 (i.e., > 42 days), the value will be defined to be 43 days. For each participant, linear and bilinear regression models will be fit, and the better fit model based on lower AIC similarly as described for BACFU(0-14) in [Section 11.1.1](#) will be used to estimate BATTP(0-14), BATTP(0-2) and BATTP(2-14) of TTP from Screening to Day 14, Screening to Day 2 and Day 2 to Day 14, respectively. BATTP(0-14), BATTP(0-2) and BATTP(2-14) will be analyzed using an ANCOVA model, with a fixed effect for treatment group and baseline TTP as a covariate. An ANCOVA model will be used to quantify the evidence that each of the treatment group mean BATTP(0-14), BATTP(0-2) and BATTP(2-14) is less than 0.

Mean and mean change from baseline of TTP with 95% CI at each time point will be presented in line plots by treatment group. In addition, observed and fitted lines of bilinear and linear regression models of TTP over time will be presented for each participant.

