11.2.2 Sputum Lipoarabinomannan

When a value of concentration of sputum LAM is < lower limit of quantification (LLOQ), the value will be defined to be half of LLOQ. For each participant, linear and bilinear regression models will be fit, and the better fit model based on lower AIC similarly as described for BACFU(0-14) in [Section 11.1.1](#) will be used to estimate BALAM(0-14), BALAM(0-2) and BALAM(2-14) of log concentration of sputum LAM from Screening to Day 14, Screening to Day 2 and Day 2 to Day 14, respectively. BALAM(0-14), BALAM(0-2) and BALAM(2-14) will be analyzed using an ANCOVA model, with a fixed effect for treatment group and baseline log value of concentration of sputum LAM as a covariate. An ANCOVA model will be used to quantify the evidence that each of treatment group mean BALAM(0-14), BALAM(0-2) and BALAM(2-14) is less than 0.

Geometric mean and geometric mean ratio of post-baseline to baseline of concentration of sputum LAM with 95% CI at each time point will be presented in line plots by treatment group. In addition, observed and fitted lines of bilinear and linear regression models of log concentration of sputum LAM over time will be presented for each participant.

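### The one-sided test for time to positivity points the wrong way: a working drug lengthens TTP, but the plan tests whether the TTP slope is below zero

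*SAP*

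**What the plan says.** SAP 5.2 (Table 2) defines the TTP endpoints as plain slopes, for example "Slope of the TTP in the MGIT system from Day 2 to Day 14". SAP 11.2.1 fixes the direction of the scale: when a culture "is not concluded by Day 42 (i.e., > 42 days), the value will be defined to be 43 days". The same section then seeks "evidence that each of the treatment group mean BATTP(0-14), BATTP(0-2) and BATTP(2-14) is less than 0". Protocol 9.4, Table 9, agrees, asking whether "the each of the treatment group means $BA_{TTP}(0-14)$, $BA_{TTP}(0-2)$ and $BA_{TTP}(2-14)$ is less than 0".

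The other two markers use the same direction. For LAM, SAP 11.2.2 asks whether "each of treatment group mean BALAM(0-14), BALAM(0-2) and BALAM(2-14) is less than 0". For CFU, SAP 11.1.1 asks whether the group mean is "less than 0 (i.e., that the treatment group mean has a negative slope on average".

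The SAP contains two sign conventions for the individual fits:

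- **Printed models (SAP 11.1.1, repeated with the node fixed at 2 in 11.1.2):** "\log_{10} CFU/mL = \alpha - \beta_1 \cdot t", with BA set equal to the estimated beta. A falling response then has a positive BA.
- **Code (SAP Appendix 4):** the mean is alpha plus beta times day, and the ANCOVA takes one-sided p-values with the LOWER option. A falling response then has a negative BA. SAP 9.1 refers to this appendix for the code to be used.

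On the status of the TTP tests, SAP 11.1.2 states: "There will be no adjustment for multiple comparisons and no formal success criteria for all secondary EBA measurements".

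**The concern.** TTP moves in the opposite direction to CFU and LAM when treatment works: fewer bacilli mean a longer time to a positive culture. One instruction to look for values below zero therefore cannot suit all three markers. If TTP is analysed as the slope it is defined to be, the stated test gives a one-sided p-value above 0.5 whenever the estimated slope is positive, and the value approaches 1 as the drug works better. This applies to HRZE as well as to every TBA-7371 regimen.

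Protocol 4.2 gives as a reason for measuring TTP that it may show whether MGIT culture can replace solid culture. A TTP p-value near 1 beside a small CFU p-value would read as disagreement between methods that in fact agree. Turning the test round after the results are known would be a post hoc change to a prespecified analysis.

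There is a second problem in the specification of the primary endpoint. The minus sign in the printed CFU models conflicts with the SAP's own reading of a negative slope as activity.

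**Working it through.** **1. Sign check on two example lines.** Take log CFU = 6 − 0.1t (falling, drug works) and TTP = 5 + 0.5t (rising, drug works).

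| Convention | BA for CFU | BA for TTP | Testing below zero is right for |
|---|---|---|---|
| Appendix 4 code: alpha + beta·day | −0.1 | +0.5 | CFU and LAM, not TTP |
| Printed models: alpha − beta·t, BA = beta | +0.1 | −0.5 | TTP, not CFU or LAM |

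The two errors cannot occur together, but one occurs under either convention.

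**2. Which convention the SAP means.** The slope definitions in 5.2, the negative-slope reading in 11.1.1, the Day 14 minus baseline formula in 11.1.3.1, the mixed model in 11.1.3.2 (time enters with a plus sign) and Appendix 4 all treat decline as negative. Only the printed equations in 11.1.1 and 11.1.2 do not. The primary CFU test is therefore correct as coded, and the TTP direction is the one that is wrong.

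**3. Reproducing the plan's own figure.** SAP 6.2 and Protocol 9.2 give 80% (90%) power for a mean BA_CFU(0-14) reduction of 0.067 (0.079), with SD 0.1, n = 15 and one-sided 5%. A one-sample t-test with 14 df has noncentrality (0.067/0.1)·√15 = 2.595 and critical value 1.761, which gives 79.4%. For 0.079 it gives 89.7%. The stated figures are reproduced, so the same calculation is used for TTP.

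**4. TTP.** The documents give no TTP effect or SD, so the true mean slope is assumed to be d between-participant SDs above zero. The noncentrality is d·√15. The ANCOVA error df are 90 − 6 groups − 1 covariate = 83, and the critical value is 1.663. The last column is P(T ≤ d·√15), the stated test's p-value when the estimate equals the true effect.

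| d | d·√15 | Rejects as written (lower tail) | Rejects in the correct (upper) tail | p as written |
|---|---|---|---|---|
| 0.1 | 0.387 | 2.1% | 10% | 0.65 |
| 0.3 | 1.162 | 0.26% | 31% | 0.88 |
| 0.5 | 1.936 | 0.02% | 61% | 0.97 |
| 1.0 | 3.873 | 0.000002% | 99% | 0.9999 |

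With 14 df, d = 0.5 gives 0.02% against 58%, with p = 0.96.

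**5. Simulation check** (4,000 runs, 15 participants, days 0 to 14, a linear slope per participant, standardised effect 0.67, 14 df). With the code's sign, the below-zero test rejected in 79.8% of runs for falling CFU or LAM and 0.0% for rising TTP. With the printed sign, it rejected in 0.0% and 79.7%.

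**The case against.** The strongest reply has four parts.

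- **Appendix 4 contains no TTP analysis.** Its fits model log CFU and its ANCOVA covariate is screening log CFU, so no TTP code in the SAP actually runs in the wrong tail. This is true, but SAP 11.2.1 and Protocol Table 9 state the wrong direction in words. SAP 11.2.1 also models TTP on the CFU method, for which the only ANCOVA template is lower-tailed.
- **SAP 11.2.1 refers back to 11.1.1, where the printed minus sign makes the TTP test right.** Taken literally, it does. That reading reverses the primary CFU test and the LAM test, and it contradicts the slope definition and the other places listed in step 2 of the working.
- **No accept-or-reject decision is planned for TTP.** This stands. SAP 9.1 ties the one-sided 5% level to the primary endpoint, and using it for TTP is an inference from the code template. For a given fitted mean the other tail is simply 1 − p, so no information is lost. The rejection rates show how misleading the p-value would be; they do not describe a decision the plan makes.
- **The true direction would still be visible.** This also stands. Slope estimates, confidence intervals, the planned mean-change plots and the individual fitted lines would all show TTP lengthening.

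These points limit the harm, but they do not make the stated direction correct.

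**Conclusion.** The concern holds. Under the slope definition and the sign used in the code, all three TTP slopes are tested in the wrong tail, in both the SAP and the protocol. Under the printed models, CFU and LAM would be reversed instead. At an assumed effect of 0.5 SD the stated TTP test would almost never detect activity that the correct test finds about 60% of the time.

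This rests on three assumptions: the TTP effect sizes, a one-sided 5% level carried over from the CFU template, and 15 participants per group. The direction of the error rests on none of them. It follows from the definition of TTP and the 43-day rule.

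The primary CFU test as coded is unaffected, so its printed minus sign is a conflict in the written specification and not a threat to the coded result. The point should be fixed before analysis, but it does not endanger the trial's main conclusion.

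**What to change.** 1. In SAP 11.2.1 and Protocol Table 9, test BA_TTP(0-14), (0-2) and (2-14) for being greater than zero.
2. Add a TTP ANCOVA block to Appendix 4 with baseline TTP as covariate and the UPPER option. The starting-value grids for the individual TTP fits also need to be on the scale of days, since the existing ones are set for log CFU.
3. Leave the CFU and LAM tests as LOWER. Switching the existing block to UPPER would break the CFU test.
4. In SAP 11.1.1 print the models as alpha + beta1·t up to the node and alpha + (beta1 − beta2)·kappa + beta2·t after it, with the linear model as alpha + beta1·t. Use the same form with kappa = 2 in 11.1.2. This is algebraically the same as Appendix 4, and a BA_CFU below zero then means decline.

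The cost is wording and one code block, with no new data and no loss of power. Changing Protocol Table 9 is an amendment and needs ethics approval (Protocol 10.1.1). If that is not practical, Protocol 10.1.7 allows changes to analyses to be placed in the SAP. The correction could then be made there alone, with SAP Section 8, which now reports no changes to the planned analyses, updated to record it.

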11.2.2 Sputum Lipoarabinomannan

When a value of concentration of sputum LAM is < lower limit of quantification (LLOQ), the value will be defined to be half of LLOQ. For each participant, linear and bilinear regression models will be fit, and the better fit model based on lower AIC similarly as described for BACFU(0-14) in [Section 11.1.1](#) will be used to estimate BALAM(0-14), BALAM(0-2) and BALAM(2-14) of log concentration of sputum LAM from Screening to Day 14, Screening to Day 2 and Day 2 to Day 14, respectively. BALAM(0-14), BALAM(0-2) and BALAM(2-14) will be analyzed using an ANCOVA model, with a fixed effect for treatment group and baseline log value of concentration of sputum LAM as a covariate. An ANCOVA model will be used to quantify the evidence that each of treatment group mean BALAM(0-14), BALAM(0-2) and BALAM(2-14) is less than 0.

Geometric mean and geometric mean ratio of post-baseline to baseline of concentration of sputum LAM with 95% CI at each time point will be presented in line plots by treatment group. In addition, observed and fitted lines of bilinear and linear regression models of log concentration of sputum LAM over time will be presented for each participant.

11.3 Subgroup Analyses

Subgroup analyses will be performed with respect to the primary efficacy variable. The subgroups will include the following:

- Sex: female and male
- Age group: <45 and \geq 45 years old
- HIV: positive and negative (using the Baseline assessment)

11.4 Interim Analysis

No formal interim analysis is planned in this trial.

Unmasked safety and (if available) PK data on each cohort will be provided to the IDMC for dose escalation recommendations.

11.5 Sensitivity Analysis

All sensitivity efficacy analyses will be performed in the per-protocol population to assess the robustness of results.

If the study identifies participants who are randomized to the HRZE treatment group with confirmed isoniazid-resistant and rifampicin susceptible tuberculosis based on the Hain test, a sensitivity analyses of efficacy endpoints will be performed in the HRZE treatment group after excluding these participants from the mITT population.

12 SAFETY ANALYSIS

All safety analyses will be performed in the Safety population.

12.1 Adverse Events

Adverse events (AEs) will be recorded from the time a participant has signed the informed consent until end of study. Each verbatim AE term will be coded to a SOC and preferred term using the most recent version of the Medical Dictionary for Regulatory Activities dictionary version 22.0 or higher. Intensity for each AE will be graded as Grade 1 (Mild), Grade 2 (Moderate), Grade 3 (Severe), Grade 4 (Potentially Life-threatening), or Grade 5 (Death) according to the Division of Acquired Immunodeficiency Syndrome (DAIDS) Table for Grading the Severity of Adult and Pediatric Adverse Events [DAIDS 2017].

If the start date of an AE is incomplete or missing, the event will be assumed to be started after day 1, unless the incomplete start date (month and/or year) or the stop date (complete or incomplete) clearly indicates that the event started before study day 1.

Summaries of system organ class (SOC) and preferred term will be sorted alphabetically by SOC and by decreasing frequency of preferred term in the all TBA-7371 group (then alphabetically for ties). If a participant has more than one AE at a given level (e.g. SOC and preferred term), the participant will only be counted once within that level.

An AE listing by participant will display all reported AEs up to end of Follow-up visit (Day 42) or the Early Withdrawal visit, and will include the verbatim term in addition to the SOC and preferred term. This listing will also include all relevant data associated with the event: e.g. date of onset, date resolved, date of first dose, date of last dose, severity, frequency, outcome, relationship to study drug, action taken with study drug, and required therapy. When a date is presented, the study day associated with the date will also be displayed. Separate listings will be presented for participants with serious adverse events (SAEs), participants with AEs leading to discontinuation and participants who died, if any.

